| May, 11, 2017 | 
For a sub group of participants, extensive physical examination was performed at baseline, three, and nine months. Permission obtained to repeat examination at the end-of-study visit. Permission to replace participant drop-outs. Upon the inclusion of participant number 260, drop-outs will be counted and recruitment will continue until a similar number of new participants has been
 | 
No changes concerning the primary outcome of DAGMAR
 
Ensure sufficient power in primary analysis.
 |

| | | |
|--|---|--|
| | enrolled or until the end of 2017. Replacement-participants will receive same randomization as drop-outs | |
|--|---|--|

Importance of vitamin D supplementation in patients with Graves' disease: a randomized controlled trial

Introduction

Graves' disease is one of the most frequent causes of hyperthyroidism. The disease is characterized as an autoimmune disorder, caused by stimulating antibodies directed against the thyroid gland's TSH receptor. The disease is preferably treated medically, but with a high risk of relapse, as approx. 50% of patients experience a relapse of the disease, often within one year after the end of treatment.

Vitamin D has been found to be important for the immune system and to be associated with other autoimmune disorders. The vitamin D level in the blood has been shown to be lower in patients with Graves' disease than in healthy individuals. With this study, we want to investigate how supplementation with vitamin D affects the prognosis in patients with Graves' disease.

Background

Graves' disease

Hyperthyroidism is a frequent disease in Denmark with approx. 5000 new cases per year(1). Approximately 40% of cases is caused by Graves' disease (GS), an autoimmune disease with potential reversibility. GS is characterized by the presence of autoantibodies (thyroid-stimulating immunoglobulin (TRAb)) directed against the TSH receptor, which cause increased production of thyroid hormones. Triiodothyronine (T3) is the active hormone. All the body's cells have nuclear receptors T3, and T3 regulates the transcription of many different genes. Hyperthyroidism therefore affects all organs in the body.

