Treatment with vitamin D supplementation will reduce the number of treatment failure of Graves' disease in the intervention group by 33% compared to the placebo group.

Secondary hypotheses.

Treatment with vitamin D supplements will accelerate the normalization of bone turnover and muscle balance function and shorten the time to symptom freedom.

Vitamin D supplementation reduces vascular stiffness in patients with GS.

Design

The study is conducted as a double-blind, randomized and placebo-controlled trial with a clinical follow-up time of up to three years. The participants are patients with newly diagnosed Graves' disease recruited from the hospitals in the Central Denmark Region. The study proceeds with two parallel study groups. The participants in each of the study groups take 1 tablet daily. Each tablet is either placebo or 70 micrograms of cholecalciferol. The placebo and cholecalciferol tablets are identical in appearance.

All subjects are randomized to one of the following two groups:

Group 1: 1 placebo tablet daily (50% of participants)

Group 2: 1 tablet of cholecalciferol of 70 micrograms (50% of the participants)

The study proceeds as shown in Figure 1.

After randomisation, a smaller cohort will also undergo a study program as outlined below.

Register-based follow-up studies will be carried out after 5 and 10 years on the entire cohort.

When 260 subjects have been randomized, drop-outs will be replaced until the end of 2017 when the inclusion period ends. Study closure is when the last participant has completed the study program as described in figure 1, alternatively has stopped participation in the study.

The individual participant stops taking the project medication at the latest 12 months +/- 1 month after the end of anti-thyroid treatment - possibly earlier (cf. section on withdrawal). For the individual participant, the maximum length of treatment will be 36 months.

A control cohort of 55 healthy sex- and age-matched individuals is established.

Primary outcome measures:

The primary effect measure is assessed based on whether the participants have benefited from the treatment as assessed by:

- Treatment success: No signs of hyperthyroidism 12±1 months after the end of anti-thyroid treatment. Criteria for treatment failure not met.

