- Alcohol abuse resulting in the need for treatment or hospitalization
- Lack of willingness or desire to participate in the study
- Abuse of euphoric substances
- Pregnancy at the time of inclusion

Patients who meet all inclusion criteria and none of the exclusion criteria will be invited to participate in the study.

Withdrawal

Participants will be asked to cease treatment with the project medicine when an exclusion criteria is met:

- Changed treatment strategy for hyperthyroidism (radioiodine therapy, surgery).
- Hypercalcemia or reduced kidney function
- Onset of diseases or initiation of medication intake as listed under exclusion criteria (except systemic glucocorticoid treatment due to thyroid-associated ophthalmopathy).
- Recurrence of hyperthyroidism after discontinuation of anti-thyroid treatment.

The investigator can stop the treatment for a participant if this is deemed necessary for the participant's safety.

In case of pregnancy, the participant can continue with the project medication. Participants in the intensively studied sub-cohort (n=100) will be excluded from further studies during pregnancy, due to the radiation risk associated with the scans. However, the participants can continue in the main study (n=260).

Population size

Vitamin D and relapse risk in Graves' disease

There are no previous human studies with treatment with vitamin D3 supplements. In a medical record review of 90 medical records from patients with GS treated at Region Hospital Silkeborg or Aarhus University Hospital, it was found that $P-25OHD > 45 \text{ nmol/L}$ was associated with a 60% reduced recurrence risk compared to $P-25OHD < 45 \text{ nmol/L}$ (RR 0.40, 95% CI 0.22–0.71). The study also showed a non-significantly reduced recurrence risk in patients who used vitamin D supplements compared to those who did not take such a supplement (RR 0.71; 95% CI 0.42-1.21). Power calculation: In order to show a difference in relapse risk for intervention with vitamin D compared to placebo of 33% (from 50% to 33%), a total of 260 participants must be included in the study, with 50% randomized to placebo and 50% to supplementation with vitamin D. ($\alpha=0.05$; $\beta=0.20$). Drop-outs will be replaced by the inclusion of new participants: Upon the inclusion of participant no. 260, drop-outs will be counted and replaced by the inclusion of new participant until the end of year 2017 when the Inclusion Period ends.

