The hospital pharmacy, Aarhus University Hospital, will carry out block-randomization, so that for every 4-16 participants included, there will be an equal number in each of those treated with either placebo or vitamin D supplementation. The exact size of the blocks will be unknown to the investigator. The participants are allocated consecutively. Site-randomization will be used to ensure equal randomization of study subjects at each participating department.

For each randomization number, the pharmacy supplies an opaque, sealed envelope numbered with the study's randomization number. The envelope can be opened if there is an urgent need to obtain information about which study medication the participant in question is receiving, as the envelope contains information about the contents of the tablets that the subject is taking. In this case, this is noted in the CRF, including the reason why the randomization code for the patient in question has been broken. The envelopes will be stored at Aarhus University Hospital.

The hospital pharmacy keeps a randomization list indicating the treatment group for all randomization numbers. The license is handed over to the Investigator when the experiment has been completed.

Data collection

The studies are carried out as outlined in Figure 1.

Baseline information, randomization and initiation of project medicine must begin within three months of anti-thyroid drug treatment.

For a sub-cohort of 100 patients (the first 100 subjects recruited from the outpatient clinics at the Medical Endocrinology Department, Aarhus University Hospital as well as interested participants from the regional hospitals in the central region) baseline information and the study program will be collected within four weeks after diagnosis of GS. Randomization and start-up of the project medication will take place immediately afterwards for this group.

In accordance with section 43, subsection 1 of the Health Act, participants' consent will be obtained to, via the medical charts, to collect information about treatment choice and course of GS, duration of treatment, occurrence of complications and side effects, including Graves' orbitopathy, side effects to the anti-thyroid treatment, as well as information about infections, other medical treatment, new illnesses including contact with a doctor and admissions.

Baseline

Based on medical record information, interview and questionnaire, the following will be registered in the CRF:

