The study was created on the initiative of doctors from the Department of Medical Endocrinology, Aarhus University Hospital. No one from the project group has financial interests in the study.

Expenses for the investigation will be financed by the departments involved, as fund support is also applied for.

No financial remuneration is provided to the test subjects, but possibly a transport allowance.

Study medication in the form of vitamin D and placebo is provided free of charge by the food manufacturer and dietary supplement manufacturer Orkla Health.

Figure 1. Flow-chart showing the course of treatment and investigations in the individual participants (n=260) randomized to treatment with vitamin D or similar placebo.

*In a sub-cohort of 100 participants additional measurement will be performed in terms of: blood pressure, pulse wave velocity (arterial stiffness), muscle- and balance-measurements, bone mineral density (BMD) and body composition (by DXA-scans), 3D bone microstructure (by HR pQCT- scans), and immunological analysis. From this sub-cohort 30 participants will undertake muscle and fat biopsy at baseline, 3 and 9 months.

Statistical analysis plan, final

Analyses of treatment effects will be based on the intention-to-treat principle. The first analysis will compare baseline characteristics by randomized treatment assignment to ensure that balance was achieved by the randomization. Characteristics to be examined include known risk factors for treatment failure including age, sex, smoking habits, severity of thyrotoxicosis, former use of vitamin D and baseline vitamin D status.

Differences between groups will be evaluated using a Chi Square test for categorical variables and a two-sample *t* test or Wilcoxon ranksum test, as appropriate, for continuous variables. For the primary outcome, the risk of treatment failure will be calculated as risk ratio (RR) with 95% confidence interval (CI).

With the intention-to-treat (ITT) approach, all subject who had been randomized and had received at least one dose of study medication will be included in the analysis. If study outcome is unknown, e.g. study withdrawal or exclusion, participants will be included in the ITT assuming either a *worst-case scenario* (all had treatment failure) or a *best-case scenario* (all experienced a treatment success)

In per-protocol analyses, only participants in whom outcomes can be assessed will be included.

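### Read plainly, the May 2017 rule gives each replacement participant the arm of an earlier drop-out instead of a new randomised allocation

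*Combined protocol and SAP*

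**What the plan says.** Table 2, entry of May 11, 2017, permits drop-outs to be replaced once participant 260 has been included. On allocation it says "Replacement-participants will receive same randomization as drop-outs". The reason given is "Ensure sufficient power in primary analysis". The entry has the same date as protocol version 8, so it describes the current rule and not superseded text.

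The body mentions replacement twice:

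- Design: "When 260 subjects have been randomized, drop-outs will be replaced until the end of 2017 when the inclusion period ends".
- Population size: "Upon the inclusion of participant no. 260, drop-outs will be counted and replaced by the inclusion of new participant", up to the same end date.

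Both give the trigger and the cut-off. Neither says how a replacement's arm is set.

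Procedures for randomization describes pharmacy blocks with concealed block size, and adds "The participants are allocated consecutively" and "Site-randomization will be used to ensure equal randomization of study subjects at each participating department". It does not mention replacements.

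In the final statistical analysis plan, under intention to treat (ITT), "all subject who had been randomized and had received at least one dose of study medication will be included in the analysis". A dosed drop-out therefore stays in the analysis beside the replacement. The plan also says "In per-protocol analyses, only participants in whom outcomes can be assessed will be included".

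**The concern.** On the plain reading, a late entrant's arm is inherited from a drop-out and not drawn from the site-stratified block list. The arm ratio among late entrants then equals the arm split of the drop-outs. Dropping out happens after randomisation and treatment may affect it. The protocol itself names possible routes: persistently raised calcium or creatinine can lead to exclusion from the study, and radioiodine, surgery or recurrence, which are components of the primary failure outcome, lead to stopping study medication. It does not say which of these count as a drop-out for replacement, or how a replacement is linked to a particular drop-out, for example by site.

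Two things could be at stake. The comparison is biased if drop-out differs between arms and late entrants also differ in failure risk; both conditions are needed. Concealment is weakened if a drop-out's arm is known or guessed and the link to the replacement is visible. The documents do not say whether it is.

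**Working it through.** **Inputs.** From Population size: 50% failure on placebo, 33% on vitamin D, 1:1 allocation, 260 in total, alpha 0.05, power 0.80. Assumed here: a two-sided test (sidedness is not stated for the primary outcome), the number and split of drop-outs, full replacement, and a difference δ of 0.10 to 0.20 in failure risk between late entrants and the rest. The documents give no figure for the last three. Splits are written vitamin D:placebo, and arm sizes placebo:vitamin D.

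**1. The plan's own figure.** With a pooled-variance normal approximation and mean risk 0.415,

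n per arm = [1.96 √(2 × 0.415 × 0.585) + 0.842 √(0.25 + 0.2211)]² / 0.17² = 130.7, so 131 per arm and 262 in total.

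The stated 260 is reproduced to within rounding; unpooled variance gives 256. Power at 130:130 is 79.8%.

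**2. What same-arm matching adds to power.** Power = Φ[(0.17 − 1.96 s₀)/s₁], where s₀ is the pooled and s₁ the unpooled standard error. Take 26 drop-outs (10%) split 18:8.

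| Replacement | Assessable | Power | ITT arms (all dosed, outcomes known) | Power |
|---|---|---|---|---|
| None | 122:112 | 75.3% | – | – |
| Fresh 1:1 (13 per arm) | 135:125 | 79.7% | 143:143 | 83.4% |
| Same arm | 130:130 | 79.8% | 138:148 | 83.4% |

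Replacement restores the power. Matching the arm adds about 0.1 point among assessable participants and nothing in ITT, where it unbalances the arms.

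**3. Shift in the ITT risk difference.** With v and p replacements in the vitamin D and placebo arms,

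shift = δ × [v/(130 + v) − p/(130 + p)].

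| Drop-outs | v:p | Bracket | Shift, δ = 0.10 | Shift, δ = 0.20 |
|---|---|---|---|---|
| 26 | 13:13 | 0 | 0 | 0 |
| 26 | 14:12 | 0.0972 − 0.0845 = 0.0127 | 0.13 points | 0.25 points |
| 26 | 18:8 | 0.1216 − 0.0580 = 0.0637 | 0.64 points | 1.27 points |
| 52 | 36:16 | 0.2169 − 0.1096 = 0.1073 | 1.07 points | 2.15 points |

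Under fresh 1:1 replacement the expected ITT shift is zero whatever the drop-out split.

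**4. Size against sampling error, 18:8.** The standard error at 138:148 is √(0.25/138 + 0.2211/148) = 0.0575, so the shift is 0.0064/0.0575 = 0.11 to 0.0127/0.0575 = 0.22 standard errors.

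Under the null, with 50% in both arms, the standard error is √(0.25/138 + 0.25/148) = 0.0592. The standardised shift is x = 0.108 or 0.215, and the two-sided error is Φ(−1.96 + x) + Φ(−1.96 − x) = 5.13% or 5.53%.

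**5. Per-protocol set, 18:8.** Each arm holds 130 assessable participants, so the shift is δ × (18 − 8)/130 = 0.77 to 1.54 points. Fresh 1:1 replacement gives δ × (13/125 − 13/135) = 0.08 to 0.15 points.

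**The case against.** The strongest reply concerns the reading. The protocol says without exception that all subjects are randomised to one of two groups, and it describes a single procedure. Taken normally, a general rule covers later entrants too. The same-arm reading rests on one sentence in a summary table, translated from Danish in 2022, and that sentence may only mean the same procedure. This stands as a real possibility. It does not remove the need to act, because an English reader will take the opposite meaning. If the general rule does govern, it conflicts with the plain sense of Table 2, and the two must be reconciled.

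On size, the figures need uneven drop-out and a drift in risk together. If the underlying drop-out rates are equal, a split at least as uneven as 18:8 has two-sided binomial probability of about 0.08, and 36:16 about 0.008; the average shift over chance splits is then zero. Tablets are identical, no side effects are expected, and nothing in the documents points to a drift of 10 to 20 points. All of this stands.

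It is also true that imputing unknown outcomes could matter more. If all drop-outs at 18:8 have unknown outcomes and are counted as failures, with 50% risk in both arms, the risk difference moves by (18/148 − 8/138) × 0.5 = 3.2 points. That is a separate matter and does not justify the allocation rule.

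One could object that the power comparison should use ITT, because the stated aim is the primary analysis. It has been done there too, and same-arm replacement is no better.

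Finally, the pharmacy holds the list and could assign replacements without the investigator learning the arm. No breach of blinding or concealment is shown.

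**Conclusion.** The concern holds. The only sentence on how a replacement's arm is set describes, on its plain reading, an allocation that is not random, and the body does not correct it. The expected damage is small: none with equal drop-out, and about a fifth of a standard error at the upper end of the 18:8 scenario. That scenario rests on assumed drop-out numbers, full replacement and an assumed drift in failure risk. The concealment risk is conditional and unproven. Because the rule gives up random allocation for at most about 0.1 point of power and is cheap to correct, it should be fixed. If the intended meaning was the same procedure, the bias argument falls away and only the wording needs repair.

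**What to change.** Replace the same-arm rule with one sentence under Procedures for randomization: each additional participant receives the next consecutive number on an extended, site-stratified pharmacy list. Analyse everyone as randomised. If the Danish text already means this, correct the wording in Table 2 so that it agrees.

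If replacements were enrolled under the same-arm rule, say so, flag them in the data, and report the primary analysis restricted to the originally randomised participants as a sensitivity analysis.

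The cost is one sentence, a longer pharmacy list and, if the rule was used, one extra analysis. The drawback is that final assessable arm sizes may differ by a few participants, which costs about 0.1 point of power at 135:125.

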There are very few studies of the possible clinical significance of vitamin D on the course of GS. In an unblinded study, 30 patients with GS, in addition to conventional anti-thyroid treatment with methimazole, were randomized to a daily supplement of 1.5 micrograms alfacalcidol or no alfacalcidol (33). After 24 weeks of treatment, the mean dose of methimazole was similar in the two groups. Treatment with alfacalcidol led to a significantly lower plasma concentration of total and free T3 and thyroxin (T4), while TSH was significantly higher in those who had received treatment with alfacalcidol. There was no difference in the plasma level of TRAb. Treatment with alfacalcidol led to a significant decrease in the plasma concentration of alkaline phosphatase (33). However, the clinical use of 1,25(OH)2D has been limited by hypercalcemic side effects. The fact that the activation of vitamin D from 25-hydroxyvitamin D to 1,25(OH)2D has now been shown to take place not only in the kidneys but also locally in a number of tissues, including the cells of the immune system, has increased interest in vitamin D's possible immunomodulatory properties (34). In an unpublished review of 90 medical charts from patients with GS treated at the Regional Hospital Silkeborg or the Department of Internal Medical and Endocrinology, Aarhus University

Hospital, a low plasma concentrations of 25OHD are associated with a significantly increased risk of recurrence of GS after cessation of anti-thyroid treatment. Compared to P-25OHD < 45nmol/l, a concentration > 45nmol/l was associated with a 60% reduced recurrence risk (RR 0.40; 95% CI, 0.22-0.71), while a P-25OHD concentration above compared to below 60 nmol/l was associated with a 21% (RR 0.79; 95% CI, 0.50-0.99) decreased recurrence risk. In contrast, there was no significant effect at a threshold value of 80 nmol/l (RR 1.08; 95%CI, 0.46 – 2.32). The study also showed a non-significantly reduced relapse risk in patients who used vitamin D supplements compared to those who did not take such a supplement (RR 0.71; 95%CI, 0.42 – 1.21). In the population, the overall recurrence rate was 47%.

The following describes the randomized study i).

The controlled cohort study ii) is described separately on page 18)

Purpose

To clarify the importance of vitamin D for the course of GS, as we want to test the following hypotheses:

Primary hypothesis.

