- Treatment failure is defined as: referral to radioiodine therapy, surgery, failure to taper off anti-thyroid treatment after a maximum of 24 months of treatment, or recurrence of hyperthyroidism within one year after cessation of anti-thyroid treatment.

Secondary outcome measures:

- Relapse after ending anti-thyroid treatment, defined as recurrence of hyperthyroidism within one year after cessation of anti-thyroid treatment (TSH<0.1) or new prescription of anti-thyroid drugs in the same period.
- Plasma TRAb level
- Biochemical vitamin D status
- Dose-response relationship with supplementation with vitamin D
- Occurrence of TAO/GO
- Occurrence of side effects to anti-thyroid treatment (agranulocytosis, drug rash, hepatitis, vasculitis)
- Weight changes
- Quality of life (SF36v2) + ThyPRO.
- Effects on muscle and balance function
- Effects on calcium homeostasis and bone turnover
- Effects on blood pressure and arterial stiffness measures
- Heart rate variability
- Frequency of infection (incl. consumption of antibiotics)
- Hospital admissions / number of doctor visits

Statistical analysis plan (Original)

The data analysis will be performed in accordance with "guidance on Statistical Principles for Clinical Trials" (IHC guidance E9). Primarily, differences between the placebo and vitamin D groups

are analysed. The primary effect measure is assessed based on whether the participants have benefited from the treatment as assessed by:

- Treatment success: No signs of hyperthyroidism 12±1 months after the end of anti-thyroid treatment.
- Treatment failure is defined as: referral to radioiodine therapy, surgery, failure to taper off anti-thyroid treatment after a maximum of 24 months of treatment, or recurrence of hyperthyroidism within one year after cessation of anti-thyroid treatment (TSH<0.1 or new prescription of anti-thyroid drugs).

Predefined subanalyses:

We will investigate the effect of vitamin D supplementation in relation to the vitamin D level at inclusion. Furthermore, we will examine the effect of vitamin D supplements on the group of participants who have not used supplements with vitamin D on their own initiative.

In a pre-defined subanalysis, subjects who continue anti-thyroid medication beyond 24 months due to Graves' orbitopathy will be excluded.

Differences between groups will be assessed with Fisher's Exact test or chi square test.

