Other effect measures are calculated with t-test for two independent groups or a corresponding non-parametric test, depending on the distribution of the material. A significance level of 0.05 will be used. Primarily, data will be analyzed according to the "intention-to-treat" principle, although secondarily an "on treatment" analysis will be carried out, where the degree of compliance is corrected.

The intention-to-treat population consists of all participants who have been randomized to the study and who have received at least one dose of the study medication. In the event of missing data in the Intention-to-treat analysis, "last value carried forward" will be used. In the final protocol, there will be an account of unused or omission of inauthentic data, as well as an account of reasons for any deviations from the originally planned statistical analyses.

It is planned to carry out interim analyzes when the sub-cohort of 100 subjects (which includes mainly from Aarhus University Hospital and Regional Hospital Silkeborg) has completed the entire study program. This is to ensure that this population can be included in a data analysis which will form the basis of a PhD thesis

Study population

260 patients, men and women, with newly diagnosed GS where anti-thyroid treatment is planned. Potential study participants are recruited from hospitals in Central Denmark Region in connection with patients' attendance at the outpatient clinic.

Inclusion criteria

- Newly diagnosed Graves' disease verified by TSH below the reference range and thyroxin and/or triiodothyronine (T3 and/or T4) above the upper reference range.
- Age 18 years or older
- Elevated plasma level of thyroid stimulating immunoglobulin (TRAb)

- Planned or started (< 3 months) medical anti-thyroid treatment
- Speaks and reads Danish.
- Written consent after oral and written information

Exclusion criteria

- Daily intake of vitamin D supplements of more than 10 micrograms, which the participant wishes to continue.
- A previously diagnose of hyperthyroidism
- Planned treatment with radioactive iodine or thyroidectomy
- Chronic granulomatous disease
- Significant hypercalcemia (ionized plasma calcium $> 1.40 \text{ mmol/l}$)
- Reduced kidney function (eGFR $< 45 \text{ ml/min}$)
- Regular intake of medication with known immuno-modulating effects, including systemic glucocorticoids ($>5\text{mg/day}$ for 3 months), imurel, methotrexate, TNF α -inhibiting agents.
- Active malignant disease

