Informed consent will be obtained from all participants (Appendix 8), and the study will be carried out in accordance with the applicable recommendations. Participation in the study is voluntary, and any participant can withdraw from the study at any time if they wish to do so, and the participant cannot be required to provide any explanation in this regard. All trial participants will be given a copy of the consent form.

Ethical considerations

It is the investigator's belief that any risks and side effects are minimal and are outweighed by the new knowledge that the study will be able to provide. The individual participant has no immediate benefit from his participation. Should there be a demonstrable vitamin D deficiency at the end of the experiment, the participant will be informed and guided about this.

During the planned examinations, unexpected findings may arise, e.g. non-symptom-producing diseases and conditions. If diseases and conditions requiring treatment are observed during the examinations carried out, the project participant will be offered a referral to relevant treatment.

When the study is finally completed, the participants will be sent a brief description of the study's most important results with information on whether they were treated with active medication or placebo during the study period.

After the end of the experiment, the investigator will inform the Scientific Ethics Committee for Central Denmark Region about the results obtained, observed side effects, number of patients treated, doses used and duration of dosing.

Lack of vitamin D is widespread in Denmark. The present study will elucidate the importance of a vitamin D supplement for the prognosis and symptomatology of patients with Graves' disease. If the study shows a significant effect of intervention on the recurrence rate in the cohort, this may have an impact on the future treatment of patients with Graves' disease.

Publication

The results from the study will be sought for publication in international medical journals, as both positive, negative and inconclusive results will be published. The publications are designed exclusively by the trial manager and investigator together with the other co-investigators. There are no companies or individuals who may be presumed to have commercial interests in the interests of the study that influence the results statement or the interpretation of the trial results.

Economy

[figure not shown]

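### Two compound secondary hypotheses and 14 secondary outcomes are tested at an unadjusted 0.05, with no testing order or exploratory label and, for most of them, no deciding variable or visit

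*Combined protocol and SAP*

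**What the plan says.** The Purpose section of the protocol introduces the primary and secondary hypotheses together with "we want to test the following hypotheses". The two secondary hypotheses are "Treatment with vitamin D supplements will accelerate the normalization of bone turnover and muscle balance function and shorten the time to symptom freedom" and "Vitamin D supplementation reduces vascular stiffness in patients with GS". Between them they cover four domains: bone turnover, muscle and balance, time to symptom freedom, and vascular stiffness.

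The list of secondary outcome measures has 14 entries. Many name a domain and not a variable, for example "Effects on muscle and balance function".

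For the analysis, the original statistical analysis plan says "Other effect measures are calculated with t-test for two independent groups or a corresponding non-parametric test", followed by "A significance level of 0.05 will be used". It gives no order of testing and no division of the error rate.

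The final statistical analysis plan states no significance level. Relapse is the only listed secondary outcome for which it sets out an analysis, a Cox regression. It uses the language of exploration only for the added interactions with sex, age, time since diagnosis and smoking.

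**The concern.** A hypothesis that is put forward for testing, with a significance level attached, invites a verdict of confirmed or not confirmed. Here most secondary hypotheses could be confirmed by any of several results.

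Muscle and balance show this best. The section on muscle function and balance studies gives eight measures: knee flexion and extension at two angles, grip strength, dynamic stability, the repeated chair test and the Timed Up and Go test. The sub-cohort is examined at three and nine months, and again at end of study under the May 2017 amendment. Bone has several DXA regions, HRpQCT at two sites and several turnover markers. Vascular stiffness has two devices and several measurements. Nothing says which measure or visit decides.

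If treatment failure shows no difference, the written rules still permit a statement that vitamin D speeds muscle, bone or vascular recovery on the strength of one p<0.05. A reader could not tell whether that result was the planned test of the hypothesis or one of many.

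**Working it through.** **Inputs from the documents.** The level is 0.05 per test (original statistical analysis plan). Two-sided testing is implied by the 1.96 in the bone sizing formula. There are 14 listed secondary outcomes. Two are left out of the count. Biochemical vitamin D status should differ between arms even if the supplement does nothing for the disease, and the dose-response entry is not a single two-group comparison. That leaves 14 − 2 = 12.

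**Assumptions.** One test per outcome, no true effect on any of the 12, and a common correlation ρ between the test statistics. The documents give no correlations, so ρ = 0, 0.5 and 0.8 are shown.

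**Reproducing a stated figure.** The plan gives no overall error rate. It does give 92% power for pulse wave velocity with 50 per group, SD 1.5 m/s and a difference of 1 m/s. The standardised difference is 1 / (1.5 × √(2/50)) = 3.333, and power is Φ(3.333 − 1.960) = 0.915. The stated 92% reproduces, and it uses the full unadjusted 0.05.

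**Chance of at least one p<0.05, either direction.**
- Independent tests: 1 − 0.95^m.
- Correlated tests: 1 − E[{Φ((1.96 − √ρ·U)/√(1−ρ)) − Φ((−1.96 − √ρ·U)/√(1−ρ))}^m], with U standard normal, by numerical integration.

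**Chance of at least one false benefit.** The same with only the favourable tail: 1 − 0.975^m if independent, and the second Φ term dropped if correlated.

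| Tests | Direction | ρ = 0 | ρ = 0.5 | ρ = 0.8 |
|---|---|---|---|---|
| 12 outcomes, one test each | either | 0.46 | 0.32 | 0.19 |
| 12 outcomes, one test each | benefit only | 0.26 | 0.16 | 0.09 |
| 8 muscle and balance measures, one visit | either | 0.34 | 0.25 | 0.16 |
| The same 8 at three and nine months (16 tests) | either | 0.56 | 0.37 | 0.21 |

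So the lowest two-direction figure for the 12 outcomes, 0.19, is nearly four times 0.05 (0.186 / 0.05 = 3.7).

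**What would shift these figures.** Testing several measures or visits per outcome raises them, as the last row shows. Rare events tested by Fisher's exact test, such as individual side effects of anti-thyroid drugs, lower them somewhat, because that test rarely uses its full 0.05.

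**Power if some secondaries were made confirmatory.** Take three tests at the strictest Holm step, 0.05/3 = 0.0167 (critical value 2.394), with 50 per group.
- Pulse wave velocity: Φ(3.333 − 2.394) = 0.83, from 0.92.
- Lumbar spine BMD, 2% of 0.920 = 0.0184 with SD 0.03: standardised difference 0.0184 / (0.03 × √(2/50)) = 3.067. Power is Φ(3.067 − 1.960) = 0.87 at 0.05 and Φ(3.067 − 2.394) = 0.75 at 0.0167.

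**The case against.** Several objections stand, and they limit the point.

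- **Not every outcome is undefined.** Relapse has a definition, a one-year window and a Cox analysis. Lumbar spine BMD and pulse wave velocity are named in the section on population size, though with no visit and no deciding role. The figures with the visit schedule are not reproduced in the available text, so timing of blood samples and questionnaires cannot be fully judged.
- **No single error rate follows from the documents.** A reader might infer that about a third of trials of an ineffective supplement would show a significant secondary result. That figure needs a correlation near 0.5 and counts harm as well as benefit. Only the range is defensible.
- **The ethics section is not a decision rule.** It links possible impact on practice to this condition: "If the study shows a significant effect of intervention on the recurrence rate in the cohort". A reader might infer that a secondary outcome, relapse, is meant to drive practice. But the sentence says only that there may be an impact, and the sample size section also describes the primary comparison as one of relapse risk. Loose wording for the primary outcome is a plausible reading.
- **The final plan does not clearly restate the rule.** Its sentence "Differences between groups will be evaluated using a Chi Square test for categorical variables" directly follows the paragraph on baseline balance and may describe baseline comparisons. The 0.05 rule for secondary outcomes therefore rests on the original plan.

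A more general defence is that secondary outcomes are exploratory by convention. That would do if the plan said so. Instead it presents the hypotheses as ones to be tested and sizes the sub-cohort of 100 on one of these outcomes, with α = 0.05 and β = 0.20.

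**Conclusion.** The concern holds in a limited form. The plan sets out secondary hypotheses for testing at 0.05 each and protects none of them by order, adjustment or label. For most there is also no single variable or visit that decides. For 12 null outcomes tested once each, the chance of at least one false positive in either direction is 0.19 to 0.46, and of a false benefit 0.09 to 0.26, over assumed correlations from 0.8 down to 0. The analysis of treatment failure is untouched. What is at stake is how far any secondary finding may be claimed, and the plan should settle that.

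**What to change.** State in the final statistical analysis plan that treatment failure is the only confirmatory test. State that all secondary hypotheses and outcomes are exploratory, expressly including relapse, time to symptom freedom, all sub-cohort measures and the end-of-study repeat. Report each as an estimate with a 95% confidence interval, with no claim of significance or of a confirmed hypothesis. If data by arm have already been seen, the same label can still be applied at reporting.

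This needs no patients or data and costs no power. The small downside is that no secondary result can be claimed as confirmed.

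I would not impose a Holm procedure on three chosen variables at nine months. Knee flexion is sized only for the cohort study against healthy controls, and for muscle function in the trial the protocol says it has no applicable data. Time to symptom freedom would drop out without comment. The choice of nine months has no basis in the plan, and the related muscle hypothesis in the cohort study is set at three months. If the sponsor does want confirmatory secondary claims, it must name one variable and one visit per hypothesis before seeing data by arm. It must also accept the power loss: with three tests and 50 per group, from about 92% to 83% for pulse wave velocity and from about 87% to 75% for lumbar BMD at the strictest step.
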